The Trajectory of Fetal Alcohol Spectrum Disorders (FASD) Across the Life Span: Continuing Prevention and Longitudinal Epidemiology

NCT number NCT04026620
Document Date 07/26/2024

PROTOCOL

Complete Title: The Trajectory of Fetal Alcohol Spectrum Disorders (FASD) Across the Life Span: Continuing Prevention and Longitudinal Epidemiology

Short Title: Motivational Enhancement Therapy

Drug or Device Name(s): Not Applicable

FDA IND/IDE (if applicable): Not Applicable

Sponsor: National Institute on Alcohol Abuse and Alcoholism

Protocol Date: July 26, 2024

Sponsor

National Institute on Alcohol Abuse and Alcoholism
[name]
[name]
United States

Study Principal Investigator

[name]
[name]
[contact]

Table of Contents

ABBREVIATIONS AND DEFINITIONS OF TERMS	3
PROTOCOL SYNOPSIS	4
BACKGROUND AND RATIONALE	5
STUDY OBJECTIVE	5
STUDY DESIGN	5
DATA COLLECTION AND MANAGEMENT	6
RECRUITMENT STRATEGY	6
CONSENT PROCESS	7
ADDITIONAL SAFEGUARDS FOR PREGNANT INDIVIDUALS	7
ADDITIONAL SAFEGUARDS FOR NON-ENGLISH SPEAKING INDIVIDUALS	7
PARTICIPANT SAFETY, PROTECTION, AND CONFIDENTIALITY	7
WITHDRAWL	8
STATISTICAL ANALYSIS PLAN	8
PLANS FOR PUBLICATION	8
REFERENCES	8

Abbreviations and Definitions of Terms

Abbreviation	Definition
AUDIT	Alcohol Use Disorder Identification Test
FASD	Fetal alcohol spectrum disorders
MET	Motivational Enhancement Therapy
PAE	Prenatal Alcohol Exposure
PEth	Phosphatidyl ethanol
SA	South Africa
USDTL	United States Drug Testing Laboratories, Inc.

PROTOCOL SYNOPSIS

Study Title	The Trajectory of Fetal Alcohol Spectrum Disorders (FASD) Across the Life Span: Continuing Prevention and Longitudinal Epidemiology
Principal Investigator	[name], UNC Nutrition Research Institute
Funder	National Institute on Alcohol Abuse and Alcoholism
Clinical Phase	N/A
IND/IDE #	N/A
Investigational Drug	N/A
Study Rationale	Alcohol is a known teratogen and can cause fetal alcohol spectrum disorders (FASD). Globally, FASD are a leading cause of development delays. The Western Cape Province of South Africa currently has the highest documented prevalence of FASD in the world. Effective prevention interventions are needed to reduce the number of individuals with prenatal alcohol exposure and/or who have a diagnosis within the FASD continuum.
Study Objective(s)	To determine whether there is a greater reduction in AUDIT scores from baseline to follow-up in the intervention group relative to the control group.
Study Design	Randomized trial comparing two behavioral interventions (Motivational Enhancement Therapy vs. Pamphlets Only)
Subject Population	Inclusion Criteria
key criteria for Inclusion and Exclusion:	
1. Pregnant females, 15 - 44 years of age2. Gestation age \leq20 weeks3. At risk for an alcohol-exposed pregnancy
Number Of Subjects	Up to 400 pregnant women

BACKGROUND AND RATIONALE

Alcohol is a known teratogen, and prenatal alcohol exposure (PAE) can lead to a variety of physical malformations and cognitive and behavioral impairments and/or delays. The broad range of physical and neurodevelopmental traits associated with prenatal alcohol exposure is captured under the umbrella term of fetal alcohol spectrum disorders (FASD). The prevalence of FASD has been found to be no lower than 1-5% in communities of the United States and 17 - 28% in the Western Cape Province of South Africa (SA).¹⁻⁶ Yet there are few brief interventions designed to reduce or eliminate alcohol consumption during pregnancy in order to prevent and/or reduce the number of individuals who are diagnosed within the FASD continuum.

Drinking during pregnancy in parts of the Western Cape Province of South Africa is frequently reported. Croxford and Viljoen (1999) reported that 43% of prenatal patients in Cape metropolitan areas drank during pregnancy.⁷ Concern about FASD has grown in South Africa.⁸⁻¹⁰ Studying characteristics of Western Cape Province mothers is useful for understanding high risk drinking and for designing prevention programs. FASD prevention programs in the Western Cape Province of SA can and must be built in this area.

According to the US Surgeon General, there is no known safe amount of alcohol during pregnancy. The Host, Agent, and Environment model has guided our thinking from the start of SA research. This mainstream, utilitarian, analytic tool provides a distinctive, multivariate and multi-disciplinary understanding of prenatal alcohol exposure. Principles of Motivational Interviewing¹¹ and Community-Reinforcement Approach^{12,13} have been shown efficacious in promoting behavior change (reduced alcohol consumption) in several settings.¹⁴⁻¹⁸ Ingersoll et al (2005) reported that a one-session motivational interview-based interview reduced risk for alcohol-exposed pregnancies compared to controls who received a pamphlet on women's health. Others reported greater reduction in alcohol consumption following brief interventions.¹⁸ Potential benefits of this intervention include: women reduce or stop alcohol consumption during pregnancy which results in less or no prenatal alcohol exposure to the developing fetus. Therefore, the public health burden associated with prenatal alcohol exposure is reduced.

STUDY OBJECTIVE

The purpose of the study is to determine the efficacy of a one-session, motivational enhancement therapy intervention to reduce Alcohol Use Disorder Identification Test (AUDIT) scores compared to a comparison group which only receives pamphlets on the risks associated with alcohol consumption during pregnancy.

Primary Objective: To determine whether there is a greater reduction (change) in AUDIT scores from baseline to follow-up in the intervention group relative to the comparison group.

STUDY DESIGN

Setting

The study will be carried out in a single Municipal Area and surrounding rural areas in the Western Cape Province of SA. Afrikaans, English, and Xhosa are the dominate languages in the study area.

Procedures

Pregnant women who sought prenatal care at local clinics will be screened for study eligibility. To be eligible females must be 15-44 years of age, \leq 20 weeks gestation, and at risk for having an alcohol-exposed pregnancy (e.g., drank within the past 30 days). Up to 400 women will be enrolled into the intervention study. Enrolled pregnant participants will be randomly assigned to either an intervention group or a pamphlets-only comparison group.

Intervention Group: a one-on-one session with a project officer using motivational interviewing to examine current lifestyle choices (regarding alcohol consumption) and develop a tailored change plan to identify steps the participant can take to change a current lifestyle choice. Once a participant enrolls into the Motivational Enhancement Therapy (MET) study and is randomized to the Intervention Group, each will be provided a brief MET session, provided a call in number, and monitored up to five times throughout the pregnancy.

Comparison Group (pamphlets only): receive pamphlets on the dangers of alcohol consumption during pregnancy.

Both Groups: Women in both groups will be interviewed at enrollment and 9 months follow-up. All mothers enrolled in the Intervention Group and Comparison Group will be asked to provide blood spot samples at 3 time points: 1) on the same day the antenatal screening questionnaire is completed, 2) once during the third trimester of the pregnancy (between 30- and 34 weeks gestation), and 3) within 30 days after the birth of the baby. Obtaining the blood spot samples will take about 10-15 minutes and will be performed by an experienced research staff member. Blood spots will be collected by pricking the finger with a sterile safety lancet. The collector will wear latex free gloves and use universal precautions (five small drops of blood will be collected). Blood spots will be collected on de-identified, sterile blood spot collection cards and will be shipped to United States Drug Testing Laboratories, Inc (USDTL) for processing for detection of phosphatidylethanol (PEth) levels. Infants of both groups will be assessed with standard neurodevelopmental assessments (Bayley Scales of Infant Development)²⁰ and standardized physical assessment for growth, development, and dysmorphology.^{21,22}

Randomization

Random assignment numbers will be picked via a computerized random number selection program to indicate who is assigned to the Intervention Group and who is assigned to the Comparison Group. The randomization ratio will be 1:1. There is no blinding or masking.

DATA COLLECTION AND MANAGEMENT

Data collection will be carried out in person. Data will be recorded by hand in hard copy. Forms will be kept in locked file cabinets/offices. The offices have restricted access. As needed, data will be translated to English. Data will be entered into an electronic database. Electronic databases will be stored on password-protected computers meeting University security requirements. Standard epidemiological record keeping methods will be used to protect confidentiality. Each participant will be given an identification number. Names and other identifiable information (telephone number, address) will not be included in databases.

Intellectual property and data generated under this project will be administered in accordance with institutional policies, including the NIH Data Sharing Policy and Implementation Guidance. Materials generated under the project will be disseminated in accordance with participating institutional policies.

RECRUITMENT STRATEGY

All recruitment will be carried out in person. As the first step in this process, regular, screening for alcohol problems will occur at prenatal clinics, in the field, and at the local prevention office. Women will be

asked in the screening if they would like to participate in a trial of brief Motivational Enhancement Therapy. Those females found to be in need of assistance with alcohol problems will be referred to the prevention staff for further assessment. A total of up to 400 women who screen positive for drinking will be asked if they want to be enrolled.

CONSENT PROCESS

The informed consent process will begin with the purpose of the study and a description of the study procedures. Study staff will review the consent form and orally explain the consent form to the participant. All participants will read and sign a standard consent form (in Afrikaans and/or English). A translator will be provided, if requested, at no cost to the participant. The consent process will occur in a private location (e.g., study office or another mutually agreed upon location). To ensure that participants comprehend the nature of the study, procedures, and risk/benefits, participants will be encouraged to ask questions and repeat back study expectations. A waiver of parental consent for pregnant females 15-17 is appropriate to keep the process of consent of this study consistent with South African standards of practice and regulations. Pregnant women ages 15-17 will sign the approved informed consent documents. Staff will be acquiring consent according to South African laws and regulations. No information will be withheld while obtaining consent or directing the progress of the study.

ADDITIONAL SAFEGUARDS FOR PREGNANT INDIVIDUALS

By definition, women are the major focus of this study as FASD is caused primarily by women consuming alcohol during the prenatal period. The research focuses on the general health and behavioral factors they possess which put a fetus at risk. Human subjects are protected by using standard and conservative protocols and the protection of privileged medical information. In the feedback process empathic communication is used at all times, and blaming is not allowed. Communication styles will be monitored by the research team.

ADDITIONAL SAFEGUARDS FOR NON-ENGLISH-SPEAKING INDIVIDUALS

All field staff will be bi-lingual in the two primary languages of the study community (Afrikaans and English). All study materials will be available in Afrikaans and English. If another language is requested by a study participant, a translator will be provided at no cost to the participant.

PARTICIPANT SAFETY, PROTECTION, AND CONFIDENTIALITY

The PI will be responsible for monitoring participant data for safety concerns, adverse events, and serious adverse events. Any unanticipated problems will be reported promptly in compliance with Good Clinical Practice. Staff will notify participants of new safety information as soon as possible. Women requiring additional medical attention will be given the contact information for local providers and guided to referrals by staff.

There is no prospect of benefit for the woman or the fetus involved in this research, the risk to the fetus is not greater than minimal, and the purpose of the research is the development of important biomedical knowledge which cannot be obtained by any other means. The risks to the participants of this project will be minimal. The research focuses on the general health and behavioral factors that participants may possess which put a fetus at risk. When maternal interviews are carried out, a unique consent form is signed by the female interviewee. All information from the interview is confidential. Participants are protected by using standard conservative protocols and the protection of privileged information. Screening, confidential record reviews, and some of the research activities have strict record protection protocols. Communication styles will be monitored by the research team. Consent forms are signed emphasizing the voluntary nature of the services, that they are oriented to research, and that participants can disengage from the study at any time with no penalty.

WITHDRAWL

Participants may withdraw from the study at any point. Participants who voluntarily withdraw may keep previously given incentive amount.

STATISTICAL ANALYSIS PLAN

Primary Endpoint: Change in Alcohol Use Disorder Identification Test (AUDIT) score.

Data Analysis Plan: The primary outcome is the change in AUDIT score from baseline to 9 months follow-up. Between-group mean differences and standard deviations will be compared. Data analysis will include traditional statistical analyses for group differences.

Power Analysis: The primary test is that women in the Intervention Group should show greater reduction of alcohol consumption over time than women in the Comparison Group. Main effects of time are expected because alcohol consumption should be reduced as a result of first contact. Therefore, a group (between) effect, time (within) effect, and a group by time interaction will be explored. With a sample size of 400, alpha = .05, power of 0.95, there is power to detect an effect size (f) of .09. With a sample size of 200, there is power to detect an effect size of .13.

Data Integrity: Data will be subjected to standard quality control and assurance measures.

PLANS FOR PUBLICATION

Aggregate, anonymous data will be presented in standard scientific publications and conferences. The utilization of final publication information only in anonymous and aggregate form protects the identity of both individuals and communities. Groups and/or subgroups will not be small enough to allow individuals to be deductively identified.

REFERENCES

1. May, P. A. *et al.* Prevalence of Fetal Alcohol Spectrum Disorders in 4 US Communities. *J Am Med Assoc* **319**, 474–482 (2018).
2. May, P. A. *et al.* Approaching the Prevalence of the Full Spectrum of Fetal Alcohol Spectrum Disorders in a South African Population-Based Study. *Alcohol Clin Exp Res* **37**, 818–830 (2013).
3. May, P. A. *et al.* The Continuum of Fetal Alcohol Spectrum Disorders in a Community in South Africa: Prevalence and Characteristics in a Fifth Sample. *Drug Alcohol Depend* **168**, 274–286 (2016).
4. May, P. A. *et al.* The Prevalence, Child Characteristics, and Maternal Risk Factors for the Continuum of Fetal Alcohol Spectrum Disorders: A sixth Population-Based Study in the Same South African Community. *Drug Alcohol Depend* **218**, 108408 (2021).
5. May, P. A. *et al.* The Continuum of Fetal Alcohol Spectrum Disorders in Four Rural Communities in South Africa: Prevalence and Characteristics. *Drug Alcohol Depend* **159**, 207–218 (2016).
6. May, P. A. *et al.* Replication of High Fetal Alcohol Spectrum Disorders Prevalence Rates, Child Characteristics, and Maternal Risk Factors in a Second Sample of Rural Communities in South Africa. *Int J Environ Res Public Health* **14**, 522 (2017).

7. Croxford, J. & Viljoen, D. Alcohol consumption by pregnant women in the Western Cape. *South African Medical Journal* **89**, 962–965 (1999).

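### All masking is waived, although nothing stops the officer who counselled a woman from recording her 9-month AUDIT; masking the interviewer would reduce this bias but not remove it

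*Combined protocol and SAP*

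**What the plan says.** Under Study Design, the Randomization paragraph closes with "There is no blinding or masking". It is a rule without exceptions, and no reason is given for it.

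The Statistical Analysis Plan section sets the endpoint: "The primary outcome is the change in AUDIT score from baseline to 9 months follow-up". The Both Groups paragraph gives the contacts: "Women in both groups will be interviewed at enrollment and 9 months follow-up". Data Collection and Management gives the mode: "Data collection will be carried out in person. Data will be recorded by hand in hard copy".

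Contact differs by arm. A woman allocated to MET has "a one-on-one session with a project officer using motivational interviewing", makes a change plan, and is then "provided a call in number, and monitored up to five times throughout the pregnancy". A comparison woman receives pamphlets. Both arms give blood spots for phosphatidylethanol (PEth) three times, and the infants of both arms are examined.

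No section says who conducts the 9-month interview, requires that person to differ from the counsellor, or keeps the allocation from that person.

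**The concern.** The women and the officers who deliver MET cannot be masked. The outcome interviewer, the infant examiner and the analyst can be, at least in part, and the plan waives this for them too.

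As written, the officer who helped a woman plan to drink less, and who followed her through pregnancy, may later ask her how much she drinks and write down the answer. The officer knows her arm, and she has a reason to give the answer the officer hopes for. A comparison woman has no such relationship. Any resulting shift goes directly into the between-arm difference in AUDIT change, which is the whole of the primary analysis, and AUDIT data alone cannot separate it from a true effect.

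**Working it through.** **1. Scale of the planned effect.** The Power Analysis gives f = .09 for N = 400 and f = .13 for N = 200, at alpha .05 and power 0.95. For the group-by-time interaction with two groups and two measurements, the noncentrality is λ = f² × N × 2/(1 − ρ), with (1, N − 2) degrees of freedom. The correlation ρ is not stated; I assume 0.5.

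- N = 400: λ = 0.0081 × 400 × 4 = 12.96, power 94.9%. Exact 95% power needs f = 0.0903.
- N = 200: λ = 0.0169 × 200 × 4 = 13.52, power 95.5%. Exact 95% power needs f = 0.1281.

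Both stated figures reproduce at ρ = 0.5. At N = 400, ρ = 0, 0.3 and 0.7 would give f = 0.128, 0.107 and 0.070. In SDs of the change score, the N = 400 effect is d = 2√(λ/N) = 2√(12.96/400) = 0.36. This says nothing about whether masking is adequate; it only gives a yardstick for the bias.

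**2. Effect of a reporting shift.** Let b be the total differential reporting between arms, in SDs of AUDIT change, with no true effect. The documents give no value for b, so the range is assumed. With n = 200 per arm (N = 400, ratio 1:1), the test statistic is displaced by s = b/√(2/n) = b/0.1. The two-sided rejection probability is 1 − Φ(1.96 − s) + Φ(−1.96 − s).

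| b (SD) | s | False positives, 200 per arm | False positives, 100 per arm |
|---|---|---|---|
| 0 | 0 | 5.0% | 5.0% |
| 0.05 | 0.5 | 7.9% | 6.4% |
| 0.10 | 1.0 | 17.0% | 10.9% |
| 0.20 | 2.0 | 51.6% | 29.3% |
| 0.30 | 3.0 | 85.1% | 56.4% |

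The column for s applies to 200 per arm. A two-sample t test in place of the normal approximation gives 7.9%, 16.9%, 51.4% and 84.9% at 200 per arm. Against the planned 0.36 SD, shifts of 0.10 and 0.20 SD are 0.10/0.36 = 28% and 0.20/0.36 = 56%.

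**3. What masking the interviewer could recover.** Suppose the interviewer causes a share q of the shift and masking removes exactly that share. The residual is b(1 − q). At 200 per arm:

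| Total b | q = 0 | q = 0.5 | q = 1 |
|---|---|---|---|
| 0.10 | 17.0% | 7.9% | 5.0% |
| 0.20 | 51.6% | 17.0% | 5.0% |
| 0.30 | 85.1% | 32.3% | 5.0% |

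The rate returns to 5% only if the interviewer causes all of the shift. If the women's own reporting causes all of it, nothing changes. The documents give no value for q.

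**The case against.** The strongest reply is that the women know their arm whatever is done. They are told at screening that this is a trial of MET, and a counselled woman can under-report to anyone. That stands. A reader might infer that separating counsellor from interviewer would remove the bias; it would not. Nor is separation the same as masking: the allocation must also be withheld, and some women will disclose it.

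Four further limits also stand.

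- A reader might infer that counsellors do record the outcome. The documents do not say so; they only fail to prevent it. That the AUDIT is self-report taken at the interview is also an inference, though a strong one.
- The direction is not settled. Under-reporting to one's counsellor is plausible, but so is franker disclosure to a familiar officer, given that the protocol requires empathy and forbids blame. Monitoring is described only for the pregnancy, and comparison women also meet research staff for blood spots, so the contrast between arms may have weakened by 9 months.
- The 51% and 85% figures describe total differential reporting, not what this fix would recover.
- The protocol mentions a project officer, prevention staff, field staff and research staff. A reader might infer that there are enough people to rotate. These labels may cover the same people, and no headcount is given.

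PEth might seem to answer the concern, since it is objective, collected in both arms and measured by an outside laboratory from de-identified cards. However, the last sample is taken within 30 days of birth, none is tied to the 9-month interview, and the Statistical Analysis Plan section does not name PEth. It does not protect the 9-month comparison.

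**Conclusion.** The point holds in a limited form. The plan waives masking even where it is possible, and following it as written leaves part of an avoidable bias in the primary comparison. The size is unknown. Over the assumed range of 0.05 to 0.30 SD in total differential reporting, the false-positive rate at N = 400 runs from about 8% to about 85%. If the interviewer accounts for half of it, masking would bring shifts of 0.10, 0.20 and 0.30 SD down to about 8%, 17% and 32%. That is a worthwhile reduction, not a cure.

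The conclusion rests on three assumptions: that the AUDIT is taken by interview at 9 months, that any shift tends to favour MET, and that the interviewer causes some of it. The case for masking the infant examiner and the analyst is secondary, because AUDIT change is the only endpoint in the analysis plan. Those steps are included because they cost little.

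**What to change.** Replace the masking sentence in the Randomization paragraph with text such as:

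> Participants and the officers delivering MET cannot be masked. The 9-month AUDIT interview will be done, from existing staff, by someone who has not delivered MET or monitoring to that woman and who is not given her allocation; interview and infant-assessment forms will carry the ID only. Arms will be coded A/B for the analyst until the primary analysis is final.

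Participants already have identification numbers and the blood-spot cards are already de-identified, so ID-only forms fit current practice, provided the ID does not reveal the arm. No visit or procedure is added. The cost is scheduling effort, and some women will still reveal their arm. That existing staff suffice is an assumption the sponsor should confirm. The report should also state that participants' own reporting bias remains.

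### The primary comparison of AUDIT change names no adjustment for baseline AUDIT; adding it costs nothing and, with equal SDs and a pre/post correlation of .3 to .8, makes 400 women worth about 615 to 444

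*Combined protocol and SAP*

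**What the plan says.** The Data Analysis Plan defines the endpoint: "The primary outcome is the change in AUDIT score from baseline to 9 months follow-up". The method is then described as follows: "Between-group mean differences and standard deviations will be compared. Data analysis will include traditional statistical analyses for group differences". No test, model or covariate is named.

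The Power Analysis paragraph adds that "a group (between) effect, time (within) effect, and a group by time interaction will be explored", and gives the design figure: "With a sample size of 400, alpha = .05, power of 0.95, there is power to detect an effect size (f) of .09". For 200 women the corresponding effect size is .13. It states no AUDIT standard deviation, no pre/post correlation and no allowance for loss to follow-up.

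Under Study Design, Procedures, AUDIT can be measured at two times: "Women in both groups will be interviewed at enrollment and 9 months follow-up". Allocation is 1:1 and unmasked. The withdrawal section says "Participants may withdraw from the study at any point".

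**The concern.** Baseline AUDIT has to be collected to form the change score, yet the plan does not say it will be used as a covariate. Analysing raw change amounts to assuming that each extra AUDIT point at baseline carries through as exactly one extra point at 9 months. If the true slope differs from 1, the raw comparison carries avoidable noise.

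The issue is precision, not bias: under randomisation the change comparison estimates the right quantity with the right type I error. What is at stake is the width of the confidence interval, and the power that remains if women are lost before 9 months. The choice should also be fixed in advance, because the trial is unmasked and the present wording leaves several analyses open.

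**Working it through.** **Inputs from the documents.** N = 400 (and 200), 1:1 allocation, two measurements, alpha .05, power .95, f = .09 (and .13).

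**Assumptions.** F test for the interaction (sidedness is not stated). Pre/post correlation ρ and the SDs at baseline (s1) and follow-up (s2) are not given, so they are varied.

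**Step 1: reproduce the plan's figures.** For the group-by-time interaction with two groups and two times, the noncentrality is λ = f² × N × 2 / (1 − ρ), with 1 and N − 2 degrees of freedom. Power of .95 needs λ = 13.06 (N = 400) or 13.12 (N = 200). At ρ = .5:

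- N = 400: detectable f = √(13.06 × .5 / 800) = .0903 (plan: .09)
- N = 200: detectable f = √(13.12 × .5 / 400) = .1281 (plan: .13)

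Allowing for rounding, both figures hold together for ρ of about .45 to .52. At N = 400 the between-group main effect (f = .157 at ρ = .5) and a one-way ANOVA (f = .181) do not reproduce .09. The power statement therefore fits the unadjusted interaction test. With complete data at two times, that is the change-score test.

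**Step 2: compare variances.** Per woman:

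- Change: s1² + s2² − 2ρ s1 s2
- Baseline-adjusted: s2² (1 − ρ²)
- Difference: (s1 − ρ s2)², never negative, and zero only when the slope ρ s2 / s1 equals 1

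With s1 = s2, the ratio adjusted/change is (1 + ρ)/2, so 400 adjusted women are worth 400 × 2/(1 + ρ) analysed by raw change.

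| ρ | Ratio | 400 adjusted women are worth |
|---|---|---|
| .3 | 0.65 | 615 |
| .5 | 0.75 | 533 |
| .8 | 0.90 | 444 |

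Over ρ = .45 to .52 the ratio is 0.725 to 0.76, and the equivalent is 552 to 526. At ρ = .5, 300 adjusted women match 400 by change, and the confidence interval is 13% narrower (√0.75 = 0.866).

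**Step 3: power at f = .09, ρ = .5, equal SDs.** For N = 400, λ = .0081 × 400 × 2 / .5 = 12.96 for change, and 12.96 / 0.75 = 17.28 adjusted. The documents give no loss rate; the rows below assume loss at random, with completers analysed.

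| Loss | Change | Adjusted |
|---|---|---|
| 0% | 0.949 | 0.986 |
| 10% | 0.926 | 0.976 |
| 20% | 0.894 | 0.960 |
| 25% | 0.874 | 0.948 |
| 30% | 0.851 | 0.934 |

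Adjustment would offset about 25% loss. For N = 200 and f = .13 with no loss, power is 0.955 against 0.988.

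**Step 4: unequal SDs.** Women enter because they drink (Recruitment Strategy: "A total of up to 400 women who screen positive for drinking will be asked if they want to be enrolled"), so equal spread at both times cannot be taken for granted. At ρ = .5:

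| s2 / s1 | Ratio | 400 adjusted women are worth |
|---|---|---|
| 0.7 | 0.47 | 860 |
| 1 | 0.75 | 533 |
| 1.25 | 0.89 | 448 |
| 1.5 | 0.96 | 415 |
| 2 | 1.00 | 400 |

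**Step 5: simulation.** In 20,000 trials with N = 400, ρ = .5, equal SDs and a difference of 4f = 0.36 SD, power was 0.947 (change) and 0.985 (adjusted), with a variance ratio of 0.743. Mean estimates were 0.359 and 0.360. Type I error was 0.049 and 0.050. With baseline as covariate, modelling change or 9-month AUDIT gave the same treatment estimate and standard error.

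**The case against.** The plan's wording does not exclude analysis of covariance, and the change-score test is valid, so this is an omission rather than an error. That is right. It limits the weight of the point but does not remove it: the only structure described, and the one that fits the power figures, is unadjusted.

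The gain at the design effect with complete data is modest, and the larger gains rest on loss rates the documents do not give. This also stands.

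Both ρ and the SDs are unknown, and the value near .5 is back-solved from rounded effect sizes. It shows which planning input fits, not how AUDIT behaves over 9 months. True. The size of the gain is conditional, from nil to more than double the sample; its direction in large samples is not.

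The equivalence of the interaction and change tests needs complete data. A likelihood mixed model would keep women with baseline only and do better than completers' change: about 0.894 against 0.874 at 25% loss, and 0.877 against 0.851 at 30%. If that is what the plan intends, the contrast under loss narrows. The adjusted analysis still has more power (0.948 and 0.934).

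**Conclusion.** The concern holds. The plan specifies no baseline adjustment for its primary comparison and so leaves open a less precise analysis, although the data for a better one are already required. With equal SDs and ρ of .3 to .8, 400 women would be worth about 615 to 444; at ρ = .5, 533. Power at f = .09 goes from about 0.95 to 0.986 with complete data, and from 0.874 to 0.948 with 25% random loss among completers analysed by change. These figures rest on assumed SDs and correlation. The gain approaches nil when the slope of follow-up on baseline approaches 1, but adjustment costs no precision in large samples. The change should be made; the trial's validity does not depend on it.

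**What to change.** State in the Data Analysis Plan that the primary analysis is a linear model of AUDIT change (or, equivalently, 9-month AUDIT) on randomised group with baseline AUDIT as covariate, at two-sided alpha .05, reporting the adjusted mean difference with its 95% confidence interval. Mean change by group can still be reported descriptively.

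As a minor clarification, add that the repeated-measures group (between) effect is not evidence of a treatment effect, because it averages in AUDIT from before randomisation.

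The cost is one or two sentences for the model and a further line for the clarification. Endpoint, sample size and data collection are unchanged, and the extra parameter costs about one or two women's worth of information.

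### Do the recruitment cap, the enrolment cap and the power calculation all need the same 400 women, with no refusals and no losses?

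*Combined protocol and SAP*

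**What the plan says.** Three places in the combined protocol and SAP give a ceiling of 400.

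- Protocol Synopsis, Number Of Subjects: "Up to 400 pregnant women".
- Study Design, Procedures: "Up to 400 women will be enrolled into the intervention study".
- Recruitment Strategy: "A total of up to 400 women who screen positive for drinking will be asked if they want to be enrolled". Earlier in that section, with no number attached, women are asked at screening whether a trial of this kind would interest them. The 400 appears only after the step in which women needing help are referred to prevention staff for further assessment.

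Power Analysis, in the Statistical Analysis Plan, then gives two conditional statements: "With a sample size of 400, alpha = .05, power of 0.95, there is power to detect an effect size (f) of .09" and "With a sample size of 200, there is power to detect an effect size of .13".

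The endpoint needs two interviews: "The primary outcome is the change in AUDIT score from baseline to 9 months follow-up". Leaving is allowed: "Participants may withdraw from the study at any point", and the participant safety section adds that "participants can disengage from the study at any time with no penalty". The document gives no refusal rate, loss rate or inflation step, and no expected number of women with both AUDIT scores.

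**The concern.** Women asked, women enrolled and women analysed are three different counts. A woman can decline, and an enrolled woman can miss the 9-month interview. A test of change in AUDIT uses only women with both scores, at least in the simple form that the power figures imply. If 400 is read as the planned value of all three counts, acceptance and follow-up must both be complete. If only the enrolment ceiling is read that way, follow-up must still be complete.

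Two things would be at stake. Recruiting staff who read the Recruitment Strategy literally might stop after 400 invitations, while staff who read Procedures might carry on to 400 enrolments. And the 95% power at f = .09 would be quoted for more women than the trial could analyse.

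**Working it through.** **Inputs from the document.** Two arms at 1:1 (Randomization); two interviews, at enrolment and 9 months (Procedures); alpha .05, power 0.95, and the pairs N = 400 with f = .09 and N = 200 with f = .13 (Power Analysis).

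**Assumptions.** The document gives no within-woman correlation ρ and no sidedness. I take the F test of the group-by-time interaction, with N counting women who have both AUDIT scores.

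**Formulas.** With two groups and two measurements, the noncentrality is λ = 2Nf²/(1 − ρ), with 1 and N − 2 degrees of freedom. Comparing mean change between arms gives λ = Nd²/4, where d is the difference in SDs of change. At ρ = 0.5 the first becomes 4Nf², so d = 4f.

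**Reproducing the plan's figures (ρ = 0.5).**

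- N = 400, f = .09: λ = 4 × 400 × .0081 = 12.96, power 0.949. The f detectable at exactly 95% power is .0903 (d = 0.36).
- N = 200, f = .13: λ = 4 × 200 × .0169 = 13.52, power 0.955. The f detectable at 95% power is .1281 (d = 0.51).

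Both printed values are right to two decimals. Other readings do not reproduce the first: at N = 400 and f = .09 the between-group effect with ρ = 0.5 has power 0.545, and the interaction has 0.719 at ρ = 0, 0.859 at ρ = 0.3 and 0.996 at ρ = 0.7. So 400 in that sentence means 400 complete pairs, with no reserve built in.

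**Effect of fewer analysed women (ρ = 0.5; the acceptance and follow-up rates are illustrations, as the document gives none).**

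| Case | Analysed N | f at 95% power | Power at f = .09 |
|---|---|---|---|
| No loss | 400 | .090 | 0.949 |
| 400 enrolled, 80% followed | 400 × .8 = 320 | .101 | 0.894 |
| 400 asked, 80% accept, 80% followed | 400 × .8 × .8 = 256 | .113 | 0.818 |
| Second printed scenario | 200 | .128 | 0.717 |
| 400 asked, 70% accept, 70% followed | 400 × .7 × .7 = 196 | .129 | 0.708 |

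Each shortfall case gives a detectable f between the printed .09 and .13. At f = .09, power of at least 0.90 needs 327 women (327/400 = 82%) and at least 0.80 needs 245 (245/400 = 61%).

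**A threshold that should not carry weight.** At ρ = 0.5 the detectable f still rounds to .09 with 362 women, 90.5% of 400. But both printed values round correctly for any ρ from about .448 to .523, and over that range the threshold runs from 400 women (100%) down to about 346 (86.5%). It shows where a two-decimal figure rounds; it is not a retention requirement.

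**The case for a change.** The strongest case for a change is that ceilings make matters worse. If no more than 400 may be asked, or enrolled, then any refusal or loss leaves fewer than 400 analysed and nothing in the plan allows replacement. With 80% acceptance and 80% follow-up, analysing 400 would take 400/.8 = 500 enrolled and 500/.8 = 625 asked, both above the ceiling. The 200-woman scenario is not described as an allowance for attrition, and it concerns a difference about 1.42 times as large (0.5123/0.3614). A reader cannot tell which number the trial expects to analyse.

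Much of this stands as description. Asked and enrolled do share one number, and no expected analysed number is given. What does not stand is that the plan contradicts itself or promises 400 analysed women. A figure qualified as a maximum is not broken by falling short of it. The power sentence says what 400 women could detect; nowhere is f = .09 named as the effect the trial must be able to find, so a shortfall misses no stated target. The Recruitment Strategy contains no rule to stop after 400 invitations, and its count comes after an uncapped question about interest. The Synopsis and Procedures both treat 400 as participants, which is the natural reading of the looser sentence.

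**Conclusion.** The concern does not call for a change. The three uses of 400 are two kinds of ceiling and one conditional calculation. They are compatible, and the calculation reproduces for N women with both scores and a correlation near 0.5, which is inferred from the printed values and not stated in the document.

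The practical effect is modest. With 320 analysed women the effect detectable at 95% power is about .10, and with 256 about .11, compared with .09 at 400. The document already shows the consequence of halving the number. Power at f = .09 remains at least 0.80 down to 245 women, a shortfall of 155/400 = 39%. The comparison of AUDIT change does not depend on which ceiling staff follow; only its precision does.

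What remains is loose wording on asked and enrolled, and an unstated expected number of complete pairs. The investigators can read the first from Procedures. The document gives no rate from which to supply the second, so a revision could add only blanks or guesses, with no gain for the analysis.
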